7 SAFETY MANAGEMENT

7.1 Risks to Human Subjects

The placement of the esophageal balloon catheter in carefully selected patients (see exclusion criteria above) confers minimal risk to the patient (such as trauma to the nasopharynx, esophageal irritation, stimulation of cough or vomiting). Adverse events possibly related to mechanical ventilation and PEEP titration will be defined as barotrauma, pneumothorax, and hypotension thought to be related to changes in mechanical ventilation. Despite these theoretical concerns, no adverse effects were seen in a small randomized trial using an esophageal balloon to titrate to optimal PEEP in patients with ARDS (2).

7.2 Safety Monitoring

Data will be collected 5 minutes after the intervention, giving time for pressure equilibration from the ventilator and its effect on ICP, CPP, and MAP. Significant changes in these metrics, as defined above, will be reported as adverse events. At the conclusion of the intervention, PEEP management will be returned to the primary team. In patients whom they continue the “optimal PEEP” level, we will continue to evaluate for possible adverse events for an additional 24 hours, and this data will be reported. In addition to clinically significant changes in ICP, CPP, and MAP as defined above, additional adverse events that will be reported will include evidence of new barotrauma, change in pressor requirement, or change in HR to > 120 or < 50 .

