2.1 Primary Objective

To determine that titration of PEEP to optimal PEEP does not result in clinically significant changes in ICP (defined as an increase in ICP > 4 mm Hg).

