5 STUDY EVALUATIONS AND MEASUREMENTS

	Pre-Intervention	Post-Intervention	Hourly x 24 Hours*
ICP	X	X	X
CPP	X	X	X
MAP	X	X	X
HR	X	X	X
SpO ₂	X	X	X
FiO ₂	X	X	X
PEEP	X	X	X
P _{tp}	X	X	
P _{aw}	X	X	
P _{es}	X	X	
Age	X		
BMI	X		
Diagnosis	X		

*Hourly data collected in patients who are continued on "optimal PEEP at the discretion of the primary team.

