6.2 Secondary Endpoints

1. CPP before and after intervention.
2. MAP before and after intervention.
3. Adverse events will be evaluated by the frequency, type, and severity, and these data will be reported

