6.4 Sample Size and Power

Based on a non-inferiority trial design using a one-sided 95% confidence interval, a power of 80%, a non-inferiority limit of 4 mm Hg for ICP, and a standard deviation of 4.4 mm Hg based on previously published data (11), the study will need 15 participants who require a change in PEEP based on esophageal balloon measurements. To evaluate our secondary goals, using a non-inferiority limit of 10 mm Hg for CPP and a standard deviation of 11.3, we would need 16 subjects, and using a non-inferiority limit of 10 mm Hg for MAP and a standard deviation of 11.8, we would need 18 subjects.

Since we estimate that 29% will not need a change in PEEP (2), we expect we will need to enroll 25 participants and obtain esophageal balloon pressure measurements in order to have 18 participants requiring changes in PEEP.

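### The adverse-event rules count any pressor change, including weaning, and reuse the mean margins as single-patient limits with no background rate, so the event frequency cannot be attributed to PEEP

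*Combined protocol and SAP*

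**What the plan says.** Section 7.2 of the combined protocol and SAP states: "Significant changes in these metrics, as defined above, will be reported as adverse events". The definitions it points back to are in Sections 2.1 and 2.2. The ICP event is "defined as an increase in ICP > 4 mm Hg", the CPP event is written as a rise of more than 10 mm Hg, and the MAP event is a fall of more than 10 mm Hg. Section 6.3 uses limits of the same size to judge the confidence bound on the mean change.

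Section 7.2 also lists "evidence of new barotrauma, change in pressor requirement, or change in HR to > 120 or < 50". Under Section 7.3, a patient who meets any one of these criteria has a possible adverse event.

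The same criteria run for a further 24 hours in some patients. The footnote to the Section 5 table begins "Hourly data collected in patients who are continued on" and limits these readings to patients whose primary team keeps the titrated PEEP. Section 3.2 expects them to be few.

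Section 6.2 makes this a secondary endpoint: "Adverse events will be evaluated by the frequency, type, and severity".

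**The concern.** There are three weaknesses in how events are counted.

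- **Pressor criterion.** It has no direction, size or time window. A patient whose pressor is reduced meets it just as a patient whose pressor is raised does, so an improvement is counted as harm.
- **Limits.** A margin for a mean across patients is a different thing from a limit for one patient. A mean over 18 patients varies far less than one patient's change, so a limit suited to the first may be crossed by ordinary fluctuation in the second.
- **Nothing to read the count against.** The trial has one arm. For the hourly readings the plan does not say which value a change is measured from, and it collects no rate of crossings at standard PEEP.

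The study's purpose is safety. If the event frequency mixes PEEP effects, background variation and pressor weaning, it supports neither reassurance nor alarm.

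**Working it through.** **Inputs.** Limits of 4, 10 and 10 mm Hg come from Sections 2.1, 2.2 and 6.3. SDs of 4.4, 11.3 and 11.8 mm Hg come from Section 6.4, which gives "a non-inferiority limit of 4 mm Hg for ICP, and a standard deviation of 4.4 mm Hg based on previously published data (11" and, for CPP, "using a non-inferiority limit of 10 mm Hg for CPP and a standard deviation of 11.3, we would need 16 subjects". Section 6.4 does not say whether these are SDs of a single level or of a within-patient change.

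**Step 1: reproduce the plan's sample sizes.** With one-sided 5%, power 80% and no true difference, the two-independent-sample formula is n = 2 × (SD × (1.645 + 0.842) / margin)².

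- ICP: 2 × (4.4 × 2.487 / 4)² = 14.96, so 15.
- CPP: 2 × (11.3 × 2.487 / 10)² = 15.8, so 16.
- MAP: 2 × (11.8 × 2.487 / 10)² = 17.2, so 18.

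All three match Section 6.4. The one-sample (paired) version, without the factor 2, gives 8, 8 and 9 and does not match. The calculation therefore uses these figures as SDs of a level.

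**Step 2: limits against SDs.** 4/4.4 = 0.91; 10/11.3 = 0.88; 10/11.8 = 0.85.

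**Step 3: chance crossings at 5 minutes with no PEEP effect.** SD of change = SD × √(2(1 − ρ)), where ρ is the before-after correlation, an assumption. For one metric, the chance is 1 − Φ(limit / SD of change). For any of the three, CPP = MAP − ICP, CPP is taken as a fall, and changes are simulated as normal. The ICP-MAP correlation implied by the three SDs is (11.8² + 4.4² − 11.3²) / (2 × 11.8 × 4.4) = 0.30.

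| ρ | ICP | CPP | MAP | Any of three |
|---|---|---|---|---|
| 0.5 | 18% | 19% | 20% | 38% |
| 0.7 | 12% | 13% | 14% | 27% |
| 0.8 | 7.5% | 8.1% | 9.0% | 18% |
| 0.9 | 2.1% | 2.4% | 2.9% | 6% |
| 0.95 | 0.2% | 0.3% | 0.4% | about 1% |

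The first row is also the result if the stated SDs are in fact SDs of change, since √(2 × 0.5) = 1. Out of 18 patients, 38% is about 7 (18 × 0.38 = 6.8) and 1% is about 0.2.

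**Step 4: direction of the CPP event.** Section 2.2(a) defines the CPP change as an increase. Section 6.3 tests a lower bound against −10 mm Hg, and the synopsis (Efficacy/Safety Evaluations) speaks of a decrease. With the Section 2.2(a) direction, the 38% in the first row becomes about 52%. The definition to which Section 7.2 refers back is therefore not settled, and the count depends on it.

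**Step 5: hourly readings (continued-PEEP patients only).** One baseline and 24 readings were simulated as an AR(1) series with no PEEP effect and hourly autocorrelation from 0 to 0.9. The chance of at least one ICP crossing is 72% to 44% if the SD of change is 4.4 mm Hg, 21% to 6% if it is 1.97, and about 0% if it is 1.0. Both the SDs and the autocorrelations are assumptions.

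**The case against.** A reader might infer that the event frequency will be high. The documents do not support that. It requires the planning SDs to be SDs of within-patient change, which Section 6.4 does not say, and Step 1 shows them used as SDs of a level. Readings minutes apart in one patient may correlate strongly, and the rate is then small.

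The plan also guards against unstable ICP. Section 3.3, exclusion 9, removes patients whose ICP varies by more than 2 cm H₂O (about 1.47 mm Hg) in the 15 minutes before intervention. If four readings had an average range of 1.47 mm Hg, the reading SD would be 1.47 / 2.059 = 0.71, the SD of change 0.71 × √2 = 1.0, and the chance of an ICP rise above 4 mm Hg below 0.01%. This stands for ICP at 5 minutes. It does not restrict MAP or CPP, or drift over 24 hours.

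Nor is a reference missing everywhere. The 5-minute reading has a pre-intervention value; the gap concerns the hourly readings and the absence of any untitrated rate. The 24-hour figures apply only to the few patients kept on the titrated PEEP.

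Finally, a sensitive trigger is defensible in a small safety study. The endpoint is descriptive, events are reported by type and severity, and under Section 7.3 an independent physician reviews each one before likely or definitely related events go to the IRB. That limits the harm. But Section 7.3 does not say that review removes events from the reported frequency, and the reviewer has no background rate to judge against.

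**Conclusion.** The point holds in a limited form. On the text alone, a reduced pressor requirement counts as a possible adverse event, mean margins serve as single-patient limits, the hourly changes lack a stated reference value, and there is no crossing rate without titration. The event frequency may therefore be substantial without any PEEP effect and cannot be attributed to PEEP.

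Its size is unknown. At 5 minutes it runs from about 1% to 38% of patients crossing any limit, for assumed correlations of 0.95 down to 0.5, with normal changes, no PEEP effect and CPP taken as a fall. The ICP exclusion could push the ICP part lower still. The primary ICP analysis and the sample size are not affected by this point.

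**What to change.** 1. In Section 7.2, replace the pressor criterion with *new pressor or increase in pressor requirement*. This changes what is reported, not how patients are managed.
2. State that hourly changes are measured from the pre-intervention value. Reconcile the direction of the CPP event between Section 2.2(a), the synopsis and Section 6.3, so that the reference back from Section 7.2 has one meaning.
3. Optionally, in patients with hourly follow-up, abstract the hourly values already charted before titration, apply the same limits, and report crossings per monitored hour before and after. Label this as descriptive context only. Patients enter when ICP and CPP are acceptable and ICP is steady, and the primary team chooses who continues, so selection and regression to the mean affect the comparison.

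Items 1 and 2 cost a few sentences. Item 3 costs some data-entry time, assumes that the unit charts these values hourly, and will yield fewer prior hours in recently monitored patients.

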7.3 Adverse Event Reporting

“Possible Adverse Event” will be defined as a patient meeting any of the above parameters. Each possible adverse event will be reviewed by a UNC critical care physician who is independent of the study within 72 hours. After independent review, events considered to be likely or definitely related to the intervention will be submitted to the IRB for review.

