2.2 Secondary Objectives

- a. To determine that titration of PEEP to “optimal PEEP” does not result in clinically significant changes in CPP (defined as an increase in CPP > 10 mm Hg).
- b. To determine that titration of PEEP to “optimal PEEP” does not result in clinically significant changes in MAP (defined as a decrease in MAP > 10 mm Hg).
- c. To report any possible adverse events after titration of PEEP.

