3.3 Study Population

Inclusion Criteria: Adult patients (age ≥ 18) admitted to the Neuro ICU of UNC Hospital requiring mechanical ventilation and with ICP monitoring in place.

Exclusion Criteria:

1. Pneumothorax or pneumomediastinum
2. Life expectancy < 24 hours or expected to require mechanical ventilation for < 24 hours
3. Condition that precludes placement of an esophageal balloon (esophageal or nasopharyngeal pathology preventing insertion of the esophageal balloon catheter, severe thrombocytopenia or coagulopathy)
4. Pre-enrollment ICP > 20 mm Hg
5. Pre-enrollment CPP < 60 mm Hg
6. Planned change in the external ventricular drain set point during the pre-intervention, intervention or post-intervention periods
7. Pregnancy
8. Incarceration
9. Variation in ICP of > 2 cm H₂O in the 15 minutes prior to intervention.

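### The adverse-event definition in Section 7.3 is tied to listed parameters and has no clinical neurological event, death or catch-all, so it is narrower than the reporting promised in objective 2.2c

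*Combined protocol and SAP*

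**What the plan says.** Section 2 and the synopsis give safety as the trial's one purpose. Among the secondary objectives, 2.2c reads "To report any possible adverse events after titration of PEEP", with no restriction on type. Section 6.2 makes adverse events an endpoint, described by frequency, type and severity.

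The definition is in 7.3: a Possible Adverse Event "will be defined as a patient meeting any of the above parameters". Each such event goes to an independent critical care physician within 72 hours. After that review, "events considered to be likely or definitely related to the intervention will be submitted to the IRB for review".

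The parameters come from two places:

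- Section 7.2, on ICP, CPP and MAP: "Significant changes in these metrics, as defined above, will be reported as adverse events". It adds "evidence of new barotrauma, change in pressor requirement, or change in HR to > 120 or < 50".
- Section 7.1: events possibly related to ventilation and titration "will be defined as barotrauma, pneumothorax, and hypotension thought to be related to changes in mechanical ventilation". It also mentions risks of placing the balloon, but as risks and not as adverse-event parameters.

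Readings are taken before the intervention and 5 minutes after the PEEP change. Hourly readings for 24 hours are taken only in patients whom the primary team keeps on the titrated PEEP (Section 5, footnote); Section 3.2 expects these to be few.

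**The concern.** Objective 2.2c is open-ended, but 7.3 gives its key term a narrower meaning. Independent review depends on that meaning, and the count in 6.2 has no other definition to use. Every item on the list is a monitored physiological value, a ventilator complication or a pressor change. A change seen at the bedside in a neurocritical care patient, such as a new neurological deterioration, qualifies only if a listed parameter is also met.

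At stake is whether the adverse-event report is complete in a small, single-group safety study. A reader of the final paper would take the count as covering any untoward event, when it covers only those on the list.

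**Working it through.** No figure in the plan needs reproducing for the main point. The check is to compare the places where an untoward event could be captured.

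1. **Definition (7.3).** Refers back to parameters. No clinical neurological event, no death, no clause for other events.
2. **List (7.1, 7.2).** ICP, CPP and MAP changes, new barotrauma, pneumothorax, hypotension, pressor change, heart rate above 120 or below 50. Again no neurological event and no death.
3. **Endpoint (6.2).** Frequency, type and severity of adverse events, with no definition of its own, so it inherits 7.3.
4. **Data table (Section 5).** ICP, CPP, MAP, HR, SpO2, FiO2, PEEP, the three pressures, age, BMI and diagnosis. No neurological observation and no vital status.
5. **Data and Safety Monitoring Plan.** Provides for 24-hour review of clinical information, but only in patients who stay on the titrated PEEP, and only to find possible adverse events, which is the term that 7.3 defines.

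An event that meets no parameter at a recorded time therefore enters none of these. The two groups of patients differ:

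- Kept on the titrated PEEP: a reading at 5 minutes, hourly readings for 24 hours, and the review of clinical information.
- Not kept on it: the 5-minute reading only.

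**Direction of the CPP change.** Section 7.2 relies on the changes as defined earlier in the protocol. Three places bear on CPP:

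- 2.2a: the clinically significant change is an increase of more than 10 mm Hg.
- Synopsis, Efficacy/Safety Evaluations: the concern is a decrease.
- 6.3: the test is that the lower bound of the change lies above -10 mm Hg, so a decrease.

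Read literally through 2.2a, a CPP fall of more than 10 mm Hg is not on the list. The consequence can be bounded if CPP = MAP - ICP, with all three read together (an assumption; the documents do not state the formula). If neither the MAP nor the ICP threshold is met, MAP has fallen by at most 10 and ICP has risen by at most 4, so CPP has fallen by at most 10 + 4 = 14 mm Hg. On the literal reading, falls above 10 and up to 14 mm Hg could therefore go uncounted. A larger fall must meet the MAP or the ICP threshold.

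**The case against.** The strongest reply is that the list already contains what matters. According to the background, earlier trials excluded these patients over concern about rising ICP and falling CPP, and changes in both are on the list. An ICP rise above 4 mm Hg in one patient is counted and reviewed. The list also goes beyond the primary analysis: that analysis tests a group mean at 5 minutes, while the list applies thresholds patient by patient, adds other events and, in some patients, uses hourly data. All of this stands and narrows the point.

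A reader might infer more than the documents support:

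- *That the brain harm this trial is about can go uncounted.* Not so where it shows as a listed change. Only events without such a change are missed.
- *That deaths would be missed.* Death is not named, but most deaths in the window would be expected to meet the MAP or heart-rate limits.
- *That events judged only possibly related are lost.* The relatedness filter in 7.3 governs IRB submission. Section 6.2 has no such filter, so these events are still reported. Whether the IRB threshold is suitable cannot be judged, because the IRB's own requirements are not in the documents.
- *That the missed share can be expressed as a rate.* The plan gives no rate for such events, and limits computed from assumed counts would not size this gap.

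Two further replies carry some weight. Section 7.2 says that reported events will include its items, which is softer than a closed list; but 7.3 is the operative definition and it reverts to parameters. Section 9 notes that most ventilated patients are sedated, so neurological change may be hard to see within an hour. That limits what the fix will find, but does not justify leaving out what is charted.

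**Conclusion.** The concern holds in limited form. As written, 7.3 narrows the promise of 2.2c: an untoward event, including a documented neurological deterioration, that meets no listed parameter at a recorded time gets no independent review and does not enter the 6.2 count. The gap matters most for patients taken off the titrated PEEP after the intervention. It does not cast doubt on the ICP analysis, and it does not mean that the plan ignores harm to the brain.

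The number of events affected cannot be derived from the documents. The conclusion assumes that 7.3 governs over the looser wording in 7.2, and that no other adverse-event route exists beyond those described. The conflict over the direction of the CPP change is a separate textual error that feeds the same definition. Under the stated assumption about CPP, its effect on the count is confined to falls above 10 and up to 14 mm Hg.

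**What to change.** In 7.3, define a Possible Adverse Event as any of the following in the observation window (the one-hour participation, plus 24 hours for patients kept on the titrated PEEP):

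- any parameter in 7.1 or 7.2;
- any new neurological deterioration documented in the ICU chart;
- death;
- any other untoward event noted by the clinical or study team.

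Send all four through the same 72-hour independent review and count them in 6.2. Reconcile 2.2a with the synopsis and 6.3 on the direction of the CPP change, since 7.2 depends on it.

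The cost is protocol wording and a look at routine ICU charting. Pressor changes and barotrauma are already on the list without appearing in the Section 5 table, so information beyond that table is needed in any case. No procedure is added and no clinical management changes. The downside is a few more events to review in about 25 patients, some of which will be hard to attribute without a control group.

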8 DATA COLLECTION AND MANAGEMENT

All patient data will be collected using REDCap through the NC TraCS system. REDCap allows for immediate data validation and range setting to reduce the likelihood of erroneous data entry. Data created for analysis will be de-identified and secured on a password protected UNC School of Medicine network hard drive. All investigators will be trained on completing the electronic case report form.

9 RECRUITMENT STRATEGY

Potential participants will be identified from daily screening of intubated patients in the NSICU by the study team. After identification of potential participants, study team members will approach the critical care team for confirmation of appropriateness and permission to enroll participants. If the clinician is agreeable, a study team member will approach the family/next-of-kin for explanation of the study.

North Carolina General Statute 90-21.13 for surrogate medical decision making to establish next of kin is as follows:

- a. Court-appointed legal guardian (except to the extent any appointed health care agent has authority, unless the health care agent's authority has been suspended by a court order).
- b. A health care power of attorney (HCPOA) may provide surrogate consent for research participation to the extent this does not contradict the written HCPOA.
- c. A durable general power of attorney, unless the research participation includes an activity expressly excluded from the power of attorney.
- d. In the event that there is neither a court appointed guardian nor an agent under a durable general power of attorney or HCPOA, surrogate consent for research may be given, as long as there is no evidence to the contrary, by the other individuals listed below, in order of priority:
 1. The subject's spouse.
 2. A majority of the subject's reasonably available parents and adult children.
 3. A majority of the subject's reasonably available adult siblings.
 4. Another individual with an established relationship with the subject who is acting in good faith on behalf of the subject and can reliably convey the subject's wishes.

Protection of Human Subjects

The patients' decision-making surrogates will be primarily approached to consent for participation in this study as most mechanically ventilated patients are medically or clinically sedated and not able to have decision making capacity. The investigators and research coordinators will approach the surrogates individually after the patients are identified as being eligible for the study to provide an informed consent process. Full disclosure will be provided that enrollment in this study will be optional and not affect major treatment decisions.

